6.2.2.2 RELATIONSHIP TO STUDY INTERVENTION

All adverse events (AEs) must have their relationship to study intervention assessed by the clinician who examines and evaluates the subject based on temporal relationship and his/her clinical judgment. The degree of certainty about causality will be graded using the categories below. In a clinical trial, the study product must always be suspect.

- **Related** – The AE is known to occur with the study intervention, there is a reasonable possibility that the study intervention caused the AE, or there is a temporal relationship between the study intervention and event. Reasonable possibility means that there is evidence to suggest a causal relationship between the study intervention and the AE.
- **Not Related** – There is not a reasonable possibility that the administration of the study intervention caused the event, there is no temporal relationship between the study intervention and event onset, or an alternate etiology has been established.

6.2.2.3 EXPECTEDNESS

The Principal Investigator will be responsible for determining whether an adverse event (AE) is expected or unexpected. An AE will be considered unexpected if the nature, severity, or frequency of the event is not consistent with the risk information previously described for the study intervention.

6.2.3 TIME PERIOD AND FREQUENCY FOR EVENT ASSESSMENT AND FOLLOW-UP

The occurrence of an adverse event (AE) or serious adverse event (SAE) may come to the attention of study personnel during study visits and interviews of a study subject presenting for medical care, or upon review by a study monitor.

All AEs including local and systemic reactions not meeting the criteria for SAEs will be captured on the appropriate case report form (CRF). Information to be collected includes event description, time of onset, clinician's assessment of severity, relationship to study product (assessed only by those with the training and authority to make a diagnosis), and time of resolution/stabilization of the event. All AEs occurring while on study must be documented appropriately regardless of relationship. All AEs will be followed to adequate resolution.

Any medical condition that is present at the time that the subject is screened will be considered as baseline and not reported as an AE. However, if the study subject's condition deteriorates at any time during the study, it will be recorded as an AE.

Changes in the severity of an AE will be documented to allow an assessment of the duration of the event at each level of severity to be performed. AEs characterized as intermittent require documentation of onset and duration of each episode.

The Study Coordinator will record all reportable events with start dates occurring any time after informed consent is obtained until 7 (for non-serious AEs) or 30 days (for SAEs) after the last day of study participation. At each study visit, the Study Coordinator will inquire about the occurrence of AE/SAEs since the last visit. Events will be followed for outcome information until resolution or stabilization.

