1.2 STUDY RATIONALE

For individuals with spinal cord injury (SCI), exercise participation reduces the risk of developing chronic cardiometabolic diseases, which are leading causes of rehospitalization and death within this population. Accordingly, recent SCI exercise guidelines have highlighted a need for exercise trials that can improve cardiometabolic factors such as glucose tolerance, blood lipids, blood pressure, and body composition. However, to date, the number of exercise trials examining these cardiometabolic outcomes in SCI is low, and these exercise regimens are often inconvenient for individuals with SCI to perform within their community. In addition to the functional impairment associated with the disability, individuals with SCI experience a number of barriers to exercise participation, such as lack of time (e.g. conflict with work schedule), accessible or usable equipment and facilities, and transportation. Thus, it is important to identify effective modes of exercise that can improve overall health but do not require a significant overall weekly time commitment. Investigators recently demonstrated that individuals with SCI could safely perform high intensity interval training (HIIT) using arm crank cycling and that as few as two days per week of HIIT could improve cardiometabolic health. Despite the advantages of HIIT, it is important to identify methods of implementing exercise trials that can successfully reach and maintain participation in larger cohorts. Recent work by the investigative group demonstrated that individuals with SCI expressed favorable perceptions of home-exercise training that incorporated telehealth technology, which allowed a fitness specialist to remotely monitor participants' training progress in real-time and provide verbal support via videoconferencing. This method of training holds even greater value for home-exercise programs that require monitoring to dose-specific protocols such as HIIT. However, the long-term success of HIIT will greatly depend on the ease at which the program can be implemented, as well as participants' adherence and perceptions of using the technology, which has not been investigated in SCI. The goal of this study is to integrate a home-based telehealth HIIT arm crank exercise training program in individuals with SCI and assess changes in cardiometabolic health and physical function. The secondary goal is to explore the uptake and implementation of HIIT in SCI. 40 participants will be randomized to home-based HIIT exercise or a no-exercise control group for 16-weeks. Body composition, aerobic fitness, muscular strength, and changes in cardiometabolic health will be assessed at baseline and 16-weeks post training. In addition to changes in cardiometabolic health outcomes, the investigators will also conduct interviews with participants to determine overall perceptions of the program, program likes and dislikes, perceived satisfaction and value, usability of equipment and technology, and factors that influence adherence.

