7 STATISTICAL CONSIDERATIONS

7.1 STATISTICAL HYPOTHESES

- Primary Efficacy Endpoint(s):
- Change in Aerobic Capacity [Time Frame: baseline]
 - All subjects will undergo a progressive peak oxygen assessment to determine aerobic capacity at the Lakeshore Foundation Exercise Physiology Facility. Subjects will be instructed to perform arm crank ergometer (Lode) at 10W for 2 min. Every 2 min thereafter, power output will be increased by 10W until voluntary fatigue. Peak aerobic power will be defined as VO₂ at the point of failure to maintain 60-65 rotations per minute.
- Change in Aerobic Capacity [Time Frame: 16weeks post training]
 - All subjects will undergo a progressive peak oxygen assessment to determine aerobic capacity at the Lakeshore Foundation Exercise Physiology Facility. Subjects will be instructed to perform arm crank ergometer (Lode) at 10W for 2 min. Every 2 min thereafter, power output will be increased by 10W until voluntary fatigue. Peak aerobic power will be defined as VO₂ at the point of failure to maintain 60-65 rotations per minute.
- Change in Muscular Strength [Time Frame: baseline]
 - Muscle Strength Assessment. Maximal load that can be lifted in one repetition (1RM) will be assessed in both limbs for chest press, elbow flexion, and shoulder flexion maneuvers.
- Change in Muscular Strength [Time Frame: 16weeks post]
 - Muscle Strength Assessment. Maximal load that can be lifted in one repetition (1RM) will be assessed in both limbs for chest press, elbow flexion, and shoulder flexion maneuvers.
- Change in Insulin Sensitivity [Time Frame: baseline]
 - Oral glucose tolerance test. Following an overnight fast each subject will consume a 75g oral glucose load within 5 min. Blood samples will be collected immediately before and 60, 90, and 120 min following glucose ingestion for measurement of serum glucose and serum insulin.
- Change in Insulin Sensitivity [Time Frame: 16weeks post training]
 - Oral glucose tolerance test. Following an overnight fast each subject will consume a 75g oral glucose load within 5 min. Blood samples will be collected immediately before and 60, 90, and 120 min following glucose ingestion for measurement of serum glucose and serum insulin.
- Change in Blood Lipids [Time Frame: baseline]
 - Laboratory analyses. Concentrations of blood lipids will be determined in the Core Laboratory of the CCTS, NORC, and DRC.
- Change in Blood Lipids [Time Frame: 16weeks post training]

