 - Laboratory analyses. Concentrations of blood lipids will be determined in the Core Laboratory of the CCTS, NORC, and DRC.
- Change in Body Composition [Time Frame: baseline]

- Dual-energy X-ray absorptiometry (DXA). Total and regional body composition will be measured by DXA (Lunar Radiation Corp., Madison, WI) at the Lakeshore Foundation Research Facility.
- Change in Body Composition [Time Frame: 16weeks post training]
 - Dual-energy X-ray absorptiometry (DXA). Total and regional body composition will be measured by DXA (Lunar Radiation Corp., Madison, WI) at the Lakeshore Foundation Research Facility.
- Change in Blood Pressure [Time Frame: baseline]
 - Systolic and Diastolic blood pressure will be assessed using standard blood pressure cuff and a stethoscope.
- Change in Blood Pressure [Time Frame: 16weeks post training]
 - Systolic and Diastolic blood pressure will be assessed using standard blood pressure cuff and a stethoscope.
- Secondary Efficacy Endpoint(s):

Semi-Structured Interview [Time Frame: 16 weeks post-training]

The semi-structured interviews will contain seven open-ended questions related to the following areas: 1) overall perceptions of the program, 2) program likes, 3) dislikes, 4) perceived satisfaction and 5) value, 6) technology and equipment usability, and 7) factors that affected adherence. These areas will be probed in greater detail by the interviewer through additional follow-up questions.

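### No planned contact asks about new adverse events in the 7-day and 30-day windows after participation ends, so capture there is passive

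*Combined protocol and SAP*

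**What the plan says.** Section 6.2.3 sets the recording period. It opens at informed consent and runs "until 7 (for non-serious AEs) or 30 days (for SAEs) after the last day of study participation".

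The same section gives one active method of finding events: "At each study visit, the Study Coordinator will inquire about the occurrence of AE/SAEs since the last visit". It also says that events may come to attention "during study visits and interviews of a study subject presenting for medical care, or upon review by a study monitor". Once an event is known, "Events will be followed for outcome information until resolution or stabilization"; section 6.2.4 has a similar rule for SAEs.

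On timing, section 1.2 says that outcomes "will be assessed at baseline and 16-weeks post training", and sections 2.1 and 4.1.1 give the same two time points. Section 7.1 places the exit interview at 16 weeks too. Among the tests that section 7.1 repeats at 16 weeks are two of maximal effort:
- the arm-crank test: "Every 2 min thereafter, power output will be increased by 10W until voluntary fatigue"
- strength: "Maximal load that can be lifted in one repetition (1RM) will be assessed in both limbs", for chest press, elbow flexion and shoulder flexion

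Section 6.1 also lists anaerobic capacity, without a time point. The synopsis (section 1.1) gives a subject duration of 6 months.

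**The concern.** The recording period extends past the last contact that the plan describes, while the only planned question is asked at a visit and concerns the time before it. An event that begins after the final visit would need a later visit to be asked about, and none is described.

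The timing makes this more than a formality. The 16-week time point brings maximal arm exertion for every participant assessed, controls included. A shoulder or elbow complaint that emerges some days after a 1RM test is the kind of non-serious event that a 7-day window exists to catch. It is also the kind least likely to lead to medical care that the study would see. If few or no events are recorded in the windows, a reader of the results could take that as evidence of safety when no one was scheduled to ask.

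**Working it through.** The plan states no figure to reproduce. The check sets the two windows against every dated contact in the documents.

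**Inputs**
- Windows: 7 days (non-serious AEs) and 30 days (SAEs) after the last day of participation (section 6.2.3).
- Active inquiry: at study visits, looking back (section 6.2.3).
- Dated assessments: baseline and 16 weeks (sections 1.2, 2.1, 4.1.1, 7.1); exit interview at 16 weeks (section 7.1).
- Telecoached training: 16 weeks (section 4.1.1), so those contacts stop then as well.
- Subject duration: 6 months (section 1.1). The last day of participation is not defined.

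**Step 1. Last described contact.** Counting from the start of the intervention, 16 × 7 = day 112.

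**Step 2. Participation ends at week 16.** The AE window closes on day 112 + 7 = 119 and the SAE window on day 112 + 30 = 142. No contact is described on or after either date.

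**Step 3. Participation ends at 6 months.** 365.25 / 2 = 182.6, about day 183. The windows close on about day 183 + 7 = 190 and day 183 + 30 = 213. The last described contact then lies 183 − 112 = 71 days (about 10 weeks) before the windows even open, less any screening and baseline time if the 6 months run from consent.

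**Step 4. Another reading of the 16-week time point.** If it meant 16 weeks after training ends, it would fall at week 32, or 32 × 7 = day 224. That exceeds 183 days, so the end of the intervention is the better reading. Even at week 32, no later contact is described.

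**Step 5. Windows as a share of the recording period.**

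| Assumed last day | AE window | SAE window |
|---|---|---|
| Day 112 | 7/119 = 5.9% | 30/142 = 21.1% |
| Day 183 | 7/190 = 3.7% | 30/213 = 14.1% |

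The first row omits the time from consent to the start of the intervention, when recording is already open, so it overstates the shares. The second row counts only the windows and not the 71 days before them. The shares depend on an undefined date, and the conclusion does not rest on them.

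**Step 6. Other ways of learning of an event.** Presentation for medical care depends on the participant seeking care where the study can see it. Monitor review depends on a record that already exists. Follow-up to resolution applies to events already known. None of these is a planned question to each participant about new events in the windows.

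**The case against.** Several stronger readings are tempting, and the documents do not support them.

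- A reader might infer that late events are recorded only if volunteered. Section 6.2.3 names two further routes, medical presentation and monitor review, and an SAE with hospitalization could surface by either. Capture is passive, not absent.
- A reader might infer that the maximal tests take place at the very last visit. There is no schedule of activities. The 16-week time point also holds a glucose tolerance test, DXA, blood pressure and an interview, and these may be spread over several days. If the exertion tests come early among them, a later visit would pick up some of their early consequences.
- A reader might infer that no contact takes place after week 16. The 6-month subject duration and the rule in section 5.1 on two missed scheduled visits leave room for contacts that are not described.
- A reader might infer that the windows cannot be filled at all. Section 6.2.3 requires recording; it does not promise that each participant will be asked.

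It is also fair to say that the exposure is limited. Training up to the final visit is covered by the inquiry there, injuries evident during testing are seen at the time, and known events are followed. Sections 7.1 and 7.3 specify no safety endpoint or safety analysis, so no planned efficacy or implementation result changes.

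All of this stands, and it narrows the point to delayed-onset events, chiefly non-serious ones for which no care is sought. It does not remove the point: nothing places a contact at the end of either window, and if undescribed contacts exist, the plan should state them.

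**Conclusion.** The point holds in a limited form. The plan commits to recording new events to 7 and 30 days after participation but describes no inquiry that reaches those days. Late non-serious events after the repeat maximal tests are likely to be under-recorded, and an empty window would not be evidence of no harm.

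The spans without planned inquiry are days 112 to 119 (AEs) and 112 to 142 (SAEs) if participation ends at week 16, counted from the start of the intervention. If it ends at 6 months, they run from day 112 to about days 190 and 213. Both readings assume that the described contacts are the only ones. The number of events that would be missed cannot be estimated, because the documents give no event rates.

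This is a worthwhile and inexpensive improvement to safety ascertainment. It is not an error in any figure of the plan and not a threat to the efficacy analysis.

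**What to change.** 1. In section 6.2.3, define the last day of study participation, for completers and for those who withdraw, and reconcile it with the 6-month subject duration in the synopsis.
2. Add two brief scripted Study Coordinator contacts, by phone or web form and identical in both arms: one just after day 7 following that date (non-serious AEs and SAEs) and one just after day 30 (SAEs). A single day-30 contact would be cheaper, but an AE that began by day 7 would have to be recalled at least 30 − 7 = 23 days later.
3. State that solicitation of new events ends at the day-30 contact, while events already known continue to be followed until resolution or stabilization. Closing the whole AE record at that contact would conflict with sections 6.2.3 and 6.2.4.

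The cost is up to 40 × 2 = 80 short contacts by existing staff and a slightly later closure of each participant's record. If participation ends at week 16, day 142 falls 183 − 142 = 41 days short of 6 months, which leaves some room for screening and baseline. If it ends at 6 months, both contacts fall after that, and the stated subject duration would need to allow for them. No dose, eligibility rule, endpoint or efficacy analysis changes.

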5 STUDY INTERVENTION DISCONTINUATION AND SUBJECT DISCONTINUATION/WITHDRAWAL

5.1 SUBJECT DISCONTINUATION/WITHDRAWAL FROM THE STUDY

Subjects are free to withdraw from participation in the study at any time upon request.

An investigator may discontinue or withdraw a subject from the study for the following reasons:

- Significant study intervention non-compliance
- If any clinical adverse event (AE), laboratory abnormality, or other medical condition or situation occurs such that continued participation in the study would not be in the best interest of the subject

Subjects who sign the informed consent form and are randomized but do not receive the study intervention may be replaced. Subjects who sign the informed consent form, and are randomized and receive the study intervention, and subsequently withdraw, or are withdrawn or discontinued from the study, will not be replaced.

A subject will be considered lost to follow-up if he or she fails to return for 2 scheduled visits and is unable to be contacted by the study site staff.

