6.2.4 ADVERSE AND SERIOUS ADVERSE EVENT REPORTING

All serious adverse events must be reported to the IRB according to regulatory requirements. The Principal Investigator will immediately report to the sponsor any serious adverse event, whether or not

considered study intervention related, including those listed in the protocol or package insert and must include an assessment of whether there is a reasonable possibility that the study intervention caused the event. Study endpoints that are serious adverse events (e.g., all-cause mortality) must be reported in accordance with the protocol unless there is evidence suggesting a causal relationship between the study intervention and the event (e.g., death from anaphylaxis). In that case, the investigator must immediately report the event to the sponsor.

All serious adverse events (SAEs) will be followed until satisfactory resolution or until the Principal Investigator deems the event to be chronic or the subject is stable. Other supporting documentation of the event may be requested and should be provided as soon as possible.

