6.3.2 UNANTICIPATED PROBLEM REPORTING

The investigator will report unanticipated problems (UPs) to the reviewing Institutional Review Board (IRB). The UP report will include the following information:

- Protocol identifying information: protocol title and number, PI’s name, and the IRB project number;
- A detailed description of the event, incident, experience, or outcome;
- An explanation of the basis for determining that the event, incident, experience, or outcome represents an UP;
- A description of any changes to the protocol or other corrective actions that have been taken or are proposed in response to the UP.

To satisfy the requirement for prompt reporting, UPs will be reported using the following timeline:

- UPs that are serious adverse events (SAEs) will be reported to the IRB within 10 working days of the investigator becoming aware of the event.
- Any other UP will be reported to the IRB within 10 working days of the investigator becoming aware of the problem.

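### New adverse events are not routinely captured beyond a 7- or 30-day tail in people withdrawn early, because section 5.1 describes no way to stop HIIT and stay in follow-up

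*Combined protocol and SAP*

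**What the plan says.** Section 6.2.3 sets the recording window by event start date. It opens at informed consent and runs "until 7 (for non-serious AEs) or 30 days (for SAEs) after the last day of study participation". The term for that last day is not defined. Active enquiry is attached to visits: "At each study visit, the Study Coordinator will inquire about the occurrence of AE/SAEs since the last visit". Events already recorded are covered separately: "All AEs will be followed to adequate resolution".

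The title of section 5 is "STUDY INTERVENTION DISCONTINUATION AND SUBJECT DISCONTINUATION/WITHDRAWAL", but its only subsection, 5.1, is about leaving the study. Besides withdrawal at the participant's request, it states: "An investigator may discontinue or withdraw a subject from the study for the following reasons". The first reason is "Significant study intervention non-compliance". The second is an adverse event, laboratory abnormality or other condition that makes continuing contrary to the person's interest. People who leave after receiving the intervention are not replaced.

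Two reporting routes carry no stated end date. Section 6.2.4 says "All serious adverse events must be reported to the IRB according to regulatory requirements". Section 6.3.2 says that unanticipated problems that are SAEs "will be reported to the IRB within 10 working days of the investigator becoming aware of the event", and gives other unanticipated problems the same time limit.

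**The concern.** The end of recording is tied to participation, not to a fixed time from randomisation. Section 5.1 makes failure to follow the intervention a ground for ending participation. A person removed at week 6 has no later scheduled visit, so nobody is due to ask about new events once the tail has passed.

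Controls have no sessions to attend, so removal for non-compliance arises mainly in HIIT. Removal for an adverse event and voluntary withdrawal can happen in either arm. If more people leave HIIT early, adverse event counts reported by arm would rest on unequal recording time. Those removed for an adverse event are also people whose later course is of safety interest.

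**Working it through.** The plan gives no figure to reproduce. The check is a reading of the text followed by date arithmetic.

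**Step 1. The texts together.** Section 5.1 ends study participation, section 6.2.3 counts 7 or 30 days from that end, and enquiry happens at visits. Sections 2.1 and 4.1.1 describe assessments only at baseline and 16 weeks. No section describes stopping HIIT while remaining in follow-up. The undefined last day reads naturally as each person's own. If it meant week 16 for everyone the gap would close, but nothing in the text supports that.

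**Step 2. Days uncovered before week 16.** Inputs: 16 weeks = 112 days (4.1.1); tails of 7 and 30 days (6.2.3). Withdrawal days are assumed and counted from the start of training. Recording ends at withdrawal day + 7 or + 30; uncovered days = 112 − that day, not below 0.

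| Withdrawal day (assumed) | Non-serious recording ends | Uncovered | SAE recording ends | Uncovered |
|---|---|---|---|---|
| 28 | 35 | 77 | 58 | 54 |
| 56 | 63 | 49 | 86 | 26 |
| 84 | 91 | 21 | 114 | 0 |

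The tail reaches day 112 only for withdrawal on or after day 112 − 7 = 105 (non-serious) or 112 − 30 = 82 (SAE).

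**Step 3. Share of a completer's window lost by one person.** Here the comparison is with a completer, who also has a tail. Tails are 7/7 = 1 week and 30/7 = 4.29 weeks. The synopsis gives a subject duration of 6 months, about 26 weeks, without saying where the 26 − 16 = 10 extra weeks fall. Three readings are possible: A, 16 weeks only; B, 10 weeks before training; C, 10 weeks after week 16. For withdrawal at training week *w*, weeks lost are 16 − *w* (A, B) or 26 − *w* (C). At *w* = 6:

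| Reading | Non-serious | SAE (upper bound) |
|---|---|---|
| A | 10/17 = 59% | 10/20.29 = 49% |
| B | 10/27 = 37% | 10/30.29 = 33% |
| C | 20/27 = 74% | 20/30.29 = 66% |

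The SAE figures are upper bounds because SAEs that staff learn of are still reported.

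**Step 4. Effect on an arm.** The 1:1 split of 40 gives 20 per arm. Full non-serious recording time is 20 × 17 = 340 person-weeks (A) or 20 × 27 = 540 (B, C). Each extra HIIT withdrawal at week 6, over the number in control, removes 10/340 = 2.9% (A), 10/540 = 1.9% (B) or 20/540 = 3.7% (C). Over weeks 4 to 12 and all three readings, the range is 4/540 = 0.7% (B, week 12) to 22/540 = 4.1% (C, week 4).

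With 4 HIIT and 2 control withdrawals at week 6, the person-weeks are:

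- A: 340 − 40 = 300 against 340 − 20 = 320 (ratio 0.938)
- B: 540 − 40 = 500 against 540 − 20 = 520 (ratio 0.962)
- C: 540 − 80 = 460 against 540 − 40 = 500 (ratio 0.920)

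HIIT time is therefore 6%, 4% or 8% lower. With 2 and 2 at the same week the ratio is 1. These are weeks eligible for recording, not weeks of active observation, since enquiry is tied to visits.

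**The case against.** The best defence is that participation plus a tail is a coherent safety window, with the same tail in both arms. Someone who leaves at week 6 is covered for all the exposure received and then for 7 or 30 days, exactly as a completer is. Non-serious events starting later may be mostly background, and adding unexposed weeks for HIIT leavers could dilute HIIT event rates. This stands as far as it goes: the 7/30-day tail is not an error. The gap comes from joining it to an exit that is described only as leaving the study. The dilution point is met by marking which events began near the last session.

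Much is also covered already. The event that prompts withdrawal, and any other ongoing event, is recorded and followed. SAEs and unanticipated problems that staff learn of remain reportable. What is left is new non-serious events after the tail, and SAEs that nobody mentions to staff.

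Section 5.1 is permissive: the investigator may withdraw someone, so staying in follow-up is not forbidden. The consent form, which is not in the material reviewed, may set terms for contact after withdrawal. Both points stand, but the exit and recording rules sit in 5.1 and 6.2.3, and neither describes continued follow-up.

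Finally, HIIT participants have up to 32 live-monitored sessions (4.1.1) and controls have none. That difference in detection may well exceed a few per cent of calendar time. This also stands, and the change proposed here does not remove it.

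**Conclusion.** The point holds as a gap in routine safety capture, and correcting it is a cheap improvement. Under the stated rules, new events after the tail are not routinely captured in people withdrawn early, and one of the grounds for removal falls mainly on HIIT.

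A reader might infer that the plan will understate the harms of HIIT, or that the trial's comparisons are biased. The documents support neither. Section 7.1 does not make adverse events an endpoint, and section 7.3 plans no comparison of them between arms, so no stated test is affected. The number and timing of withdrawals are not given, and closer monitoring may raise HIIT counts, so the size and net direction of any imbalance cannot be determined. Event rates are not given either, so no number of missed events is claimed.

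The percentages are illustrations. They assume the last day of participation is the person's own withdrawal day, withdrawal between training weeks 4 and 12, and one of three readings of the 6-month duration. If both arms lost equal numbers at equal times there would be no imbalance, though each leaver's later safety data would still be lost.

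**What to change.** 1. In section 5.1, amend the list so that intervention non-compliance and adverse events are reasons to discontinue HIIT, not to withdraw from the study. The person then stays in follow-up to the 16-week assessment, where safe, unless consent is withdrawn. The list itself must change; a sentence added beside it would contradict it. Who stops exercising remains the investigator's decision.

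2. In section 6.2.3, for every randomised participant in either arm who has not withdrawn consent, record new AEs and SAEs until the planned end of follow-up plus 7 or 30 days, or until the existing end point if that is later. The planned end is week 16 from randomisation, or the later planned last day if the 6-month duration includes follow-up after week 16. Note whether onset was within 7 or 30 days of the last session, so that on-exposure events can be shown separately.

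The cost is two wording changes and a few extra contacts by the existing Study Coordinator. Current recording is never shortened. The downsides are that some leavers will decline contact, so some safety data will still be missing, and that closer live monitoring of HIIT remains a separate imbalance.
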